2. SAFETY

The safety of infusion with the experimental product will be determined by observation of treatment emergent adverse events (TEAEs), defined as only AEs that occur after starting the trial infusion administration. In addition to TEAEs, safety will be evaluated based on the occurrence of SAEs, suspected unexpected serious adverse reactions (SUSARs), and deaths. Safety assessment in Cohorts 1 and 2 subjects will examine the cohort-specific product infusion dose and the specific FDP product type infused (e.g., FDP-CPD or FDP-ACD). The safety assessment performed in Cohort 3 subjects will assess treatment with FDP at the highest fixed infusion dose (approximately 810 mL) and compare, within the same subject, the treatment safety of FDP versus FFP at the equivalent dose.

2.1 Treatments

Each subject's infusion dose and treatment product(s) are summarized in Table 1 and discussed in this section of the statistical analysis plan (SAP). Study arm assignments are based on donor type for Cohorts

1 and 2 subjects where WB donors will be assigned to Arm 1 or Arm 3 depending on which cohort is active and plasmapheresis donors will be assigned to Arm 2 or Arm 4 depending on which cohort is active. Enrolled subjects of Arm 1 and Arm 3 will receive one or two units, respectively, of autologous FDP-CPD at a single infusion visit and those in Arm 2 and Arm 4 will receive the corresponding dose of FDP-ACD at the single infusion visit. Subjects enrolled in the Cohort 3 crossover will have two study infusion visits where they will receive separate treatments of autologous FFP at one visit and autologous FDP-ACD at the other. Randomization to one of two treatment arms just prior to the first infusion visit will indicate the specific product treatment sequence where they will be administered one of the products at the first infusion visit followed by the alternative product at the second infusion visit. See Section 3.2 for additional information regarding subject assignment and randomization.

2.1.1 Cohorts 1 and 2

All Cohort 1 subjects will receive a single infusion dose of 1 experimental product unit (approximately 270 mL) and those in Cohort 2 will receive a single infusion dose of 2 experimental FDP product units (approximately 540 mL). Subjects in Arm 1 and Arm 3 will receive the same experimental product type, FDP-CPD, but at single infusion doses of one unit and two units, respectively. Subjects in Arm 2 and Arm 4 will receive FDP-ACD instead at single infusion doses of one and two units, respectively.

2.1.2 Cohort 3

For the crossover, Cohort 3 subjects in Arm 5 and Arm 6 will receive single infusion doses of 3 autologous plasma units (approximately 810 mL) at each of their 2 infusion visits. Depending on their treatment arm, subjects will receive either the autologous experimental product (FDP-ACD) or the autologous control product (FFP) with the opposite product administered at the second scheduled infusion. Table 1 exhibits the three dose cohorts, their corresponding treatment arms, and the number of subjects needed to complete the trial.

Table 1. Dose Cohorts and Treatments

Cohort	Single Infusion Dose	Treatment	# of Subjects
1	1 unit (~270 mL)	Arm 1: FDP-CPD	4
		Arm 2: FDP-ACD	4
2	2 units (~540 mL)	Arm 3: FDP-CPD	4
		Arm 4: FDP-ACD	4
3 crossover	3 units (~810 mL/ infusion)	Arm 5: FDP-ACD x FFP	4
		Arm 6: FFP x FDP-ACD	4
Total # of Subjects			24

2.2 General Schedule for Plasma Collection, Infusion and Follow-up

There are distinct study schedules associated with subject participation. The schedules are cohort- and arm- dependent given the different plasma collection requirements of each, and for Cohort 3 the crossover design necessitating two infusion visits rather than the one infusion visit in Cohorts 1 and 2. Table 2 summarizes the number and types of study visits (e.g., collection, infusion, and follow-up) associated with the three study schedules. All of the visits are to be conducted in-person with the exception of 3 post-infusion follow-up visits that are conducted by telephone (e.g., 48-hour, 72-hour, and 14-day follow-up visits).

Table 2. Number of Study Visits by Visit Type and Treatment Arm

Study Arm	Screening Visit	Donation Type*	Collection Visit	Infusion Visit	Post-Infusion Follow-up Visits				Total # Visits
					24-hour	48 hrs, 72 hrs, and 14-day	7-day	28-day	
1	1	WB	1	1	1	3	1	1	9
2		PP	1	1	1	3	1	1	9
3		WB	2	1	1	3	1	1	10
4		PP	1	1	1	3	1	1	9
5		PP	2-3	2	2	5	2	1	15-16
6		PP	3-4	2	2	5	2	1	15-16

*WB=Whole Blood, PP=Plasmapheresis

2.2.1 Screening Visit

Individuals interested in participating must sign the study's informed consent. Subjects who consent are not enrolled, however, until eligibility is confirmed at the Screening Visit by physical examination and laboratory testing performed on the subject's collected biospecimens.

2.2.2 Collection Visit(s)

Enrolled subjects must make either autologous WB or plasmapheresis donation(s) to provide the cohort-defined volume of source plasma. A minimum interval of 7 days is required between all individual subject's plasmapheresis donations and a minimum interval of 28 days between all individual subject's WB donations.

- Arms 1 and 3.** Subjects in Arms 1 and 3 will make autologous WB donations for the manufacture of FDP-CPD. One WB collection is required of subjects in Arm 1 and two WB collections are required from subjects in Arm 3. As approved by the clinical site's Institutional Review Board (IRB), subjects, such as those in Arm 3, making more than 1 WB donation must maintain a minimum 28-day interval between donations. Subjects with a low volume donation (< 450 mL) will generally be withdrawn from the study and the collection discarded per blood center standard operating procedures (SOPs). Low volume donations in the study are never combined with other potential donations made by the study subject.

At the discretion of the PI, there may be cases where subjects making a low volume donation are allowed to make a second WB collection attempt. In such cases, however, the minimum 28-day interval between WB donations is still required.

- Arms 2, 4, 5, and 6.** Autologous plasmapheresis is the plasma collection method used for subjects in the remaining study arms. One plasmapheresis collection is adequate for the manufacture of up to two units of FDP-ACD so subjects in Arms 2 and 4 will only require a single successful collection visit. Subjects in Arms 5 and 6, however, will need to make 3 to 4 successful plasmapheresis donations to provide the minimum total plasma volume needed (approximately 1620 mL) for 3 FFP units and 3 FDP units. Approximately 10% of plasma units that are supplied for manufacturing FDP are damaged during the process and must be discarded. In those instances, the autologous plasma unit corresponding to the individual subject must be replaced, which requires the subject to return to the clinic for additional plasmapheresis to meet the required volumes for the plasma infusion visit(s).

A minimum donation interval of 7 days is required for subjects making multiple plasmapheresis donations. Subjects with a low volume donation (< 500 mL) will generally be withdrawn from the study and all low volume donations discarded per blood center SOPs; low volume donations are never

combined with other potential donations made by a subject during the study. At the discretion of the PI, there may be cases where subjects making a low volume donation are allowed a second attempt by plasmapheresis. In these cases, however, the minimum 7-day interval between donations is still required.

2.2.3 Infusion Visit(s)

The infusion visit for the first subject in each cohort is to occur approximately five weeks following his or her last collection visit. Unlike Cohorts 1 and 2 subjects, Cohort 3 subjects require two infusion visits. These are to occur with no less than a two-week interval in between infusions. Subjects will undergo autologous infusion at each of these visits according to the corresponding treatment specifications of the arm to which they belong.

2.2.4 Follow-up Visits

Post-infusion, subject assessments are to occur at scheduled in-person and telephone follow-up visits. For Cohorts 1 and 2, in-person post-infusion visits will occur on Study Days 2, 8, and 29, which corresponds to conducting assessments 24 hours, 7 days, and 28 days post-infusion. These visits will take one to two hours. Telephone follow-up visits of a 15 to 20 minute duration are to occur on Study Days 3, 4 and 15, or 48 hours, 72 hours, and 14 days post-infusion.

Follow-up visits for Cohort 3 subjects subsequent to the first infusion visit are the same as those scheduled for Cohorts 1 and 2. However, on Study Day 15, Cohort 3 subjects will undergo the second infusion and accompanying follow-up visits for this infusion are spaced in time to occur as those performed for Cohorts 1 and 2. Cohort 3 in-person follow-up visits will be scheduled for Study Days 2, 8, 16, 22, and 43 and take 1 to 2 hours to complete. The telephone follow-up visits, each taking approximately 15 to 20 minutes to complete, will be conducted on Study Days 3, 4, 17, 18, and 29.

3. PROCEDURES

3.1 Subject Identification

All consenting subjects are assigned a unique numeric subject identifier (SID). If later enrolled in the study, the SID can be used to identify individual subject's electronic Case Report Forms (CRFs). Name and date of birth will be used to identify subjects on site source documents. No personal identifiers will be used in any study associated communications or publications resulting from the research. The unique SID is to be used to identify data specific to a single subject. Representatives of the United States Army Medical Research and Materiel Command (USAMRMC), the Sponsor's Representative, the local IRB, the USAMRMC Office of Research Protections (ORP), and the Food and Drug Administration (FDA) are eligible to review medical and research records related to this study as a part of their responsibility to protect human subjects in clinical research. For such review, medical and research records will be photocopied and all personal identifiers redacted. Subjects will not receive individual study results. Aggregate findings will be published in the open literature and available by way of public record.

3.2 Randomization

Subject recruitment at Hoxworth Blood Center (HBC) will depend on accessing lists of WB and plasmapheresis donors who previously indicated an interest in participating in research. These lists of WB and plasmapheresis donors will be sorted by donation type and the center will work through the lists using a systematic scheme that represents a diverse subset of the population without bias based on race, ethnicity, gender, or age (as determined by the protocol) until the target numbers have been reached.

Research recruitment flyers are also posted at the blood center. These flyers include a telephone number for donors to call if they are interested in learning about research participation.

Depending on the activation status of recruitment for the lower dose cohorts and the version of the informed consent document that is signed, WB donors who are enrolled in the study will automatically be assigned to the FDP-CPD study arms of Cohort 1 or 2. Similarly, plasmapheresis donors who are enrolled will automatically be assigned to the FDP-ACD study arms of Cohorts 1 or 2.

For Cohort 3, which includes product crossover of FDP-ACD and FFP, only plasmapheresis donors who consent to the study are potentially eligible for study enrollment. Once enrolled, Cohort 3 subjects are randomized no more than 48 hours prior to their first infusion in a 1:1 ratio to 1 of 2 treatment arms that will determine the order in which the two plasma treatment products, FFP and FDP-ACD, are to be infused across the two study infusion visits. Based on this, some subjects will receive FFP at the first infusion visit while others will receive FDP-ACD at the first infusion visit. Cohort 3 subjects who leave the study without completing both infusion visits will be replaced; the replacement subject, assigned a unique SID, will be assigned to the same treatment arm as the discontinued subject.

The randomization list allows for over-enrollments and additional randomization slots to compensate for subjects who discontinue early. The Westat Statistician is responsible for the randomization assignments performed via the study website [<https://www.fdpcollaboration.org>]. Randomization is addressed in Section 6.6.1 of the protocol and detailed in the FDP-1 Randomization, Masking and Unmasking Plan.

3.3 Blinding/Unblinding

3.3.1 Blinding

This is a partial double-blind study. Blinding is not necessary for Cohorts 1 and 2 because they will only receive a single infusion of FDP. Cohort 3 subjects are to receive FDP at one infusion and the control product, FFP, at another. Cohort 3 subjects randomized to a treatment sequence are to remain blinded to the product they receive at each visit. The HBC Clinical Research Coordinator and 5th Floor HBC FDP research staff preparing the plasma product will be unblinded. All other HBC staff including but not limited to, the HBC PI, study subjects, RM, and 3rd Floor HBC FDP research staff involved in subject treatment will be blinded.

At Westat, the FDP-1 Clinical Operations Manager, Site Monitor, Unblinded Statistician, and Unblinded Programmers will be unblinded. All other Westat staff including but not limited to, the Project Manager (PM), Protocol Specialist, Data Manager, Data Research Associate, Project Statistician, and Project Programmers will be blinded. The Clinical Site Monitor for the Sponsor will be unblinded. All other Sponsor staff including but not limited to, the Product Manager and PVG MD will be blinded. Blinding is addressed in Section 6.6.2 of the protocol and detailed in the FDP-1 Randomization, Masking and Unmasking Plan.

3.3.2 Unblinding

Unblinding of a subject's individual randomization code is only performed for the following approved reasons:

- Medical emergency, or in the event of a serious medical condition, when knowledge of the investigational study product is essential for the clinical management or welfare of the subject;
- DSMB requests to be unmasked for subject safety review; and
- Unblinding for all reported pregnancies occurring during the study by the HBC PI.

Reasons and justification for the unblinding are to be clearly specified in the source documentation. Otherwise, unblinding is not to occur until study data are entered and cleaned, and the database is locked. Unblinding is addressed in Section 6.6.3 of the protocol and detailed in the FDP-1 Randomization, Masking and Unmasking Plan.

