For Cohort 3, which includes product crossover of FDP-ACD and FFP, only plasmapheresis donors who consent to the study are potentially eligible for study enrollment. Cohort 3 subjects are randomized no more than 48 hours prior to their first infusion in a 1:1 ratio to one of two treatment arms that will determine the order in which the two plasma treatment products, FFP and FDP-ACD, are to be infused across the two study infusion visits. Based on this, some subjects will receive FDP-ACD at the first infusion visit while others will receive FFP at the first infusion visit. Cohort 3 subjects who leave the study without completing both infusion visits will be replaced; the replacement subject, assigned a unique SID, will be assigned to the same treatment arm as the discontinued subject. The randomization list allows for over-enrollments and additional randomization slots to compensate for subjects who discontinue early. The Westat Statistician is responsible for the randomization assignments performed via the study website [https://www.fdpcollaboration.org]. Fifth floor HBC FDP research staff who randomize and prepare plasma products will complete the FDP-1 Randomization Worksheet, which contains a series of questions to verify subject eligibility. HBC FDP research staff will log on to the website and submit the worksheet information to request randomization. Shortly after the request is submitted, they will receive a confirmation email of the unmasked study arm assignment (including the randomization number). Fifth floor HBC FDP research staff will maintain records and prepare the appropriate plasma product according to the clinical site's SOPs and the study's MOP.

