### 6.6.3. Unblinding

Unblinding is not to occur until all study data are entered into the database, the data is cleaned, and the database is locked. Otherwise, unblinding of a subject's individual randomization code is only to be performed in the case of a medical emergency, or in the event of a serious medical condition, when knowledge of the investigational study product is essential for the clinical management or welfare of the subject. The reason for unblinding is to be clearly specified in the source documentation.

In the event of a medical emergency or serious medical condition, the PI should attempt to notify the sponsor prior to the request for emergency unblinding through 5th floor HBC FDP research staff. However, if the subject must be unblinded immediately, the PI will contact the study sponsor as soon as possible to report the unblinding.

Authority to request emergency unblinding is limited to the PI, RM, and the PVG MD. The PI will notify the Office of Regulated Activities, USAMMDA, Product Safety Surveillance Branch (PSSB) of the emergency unblinding as soon as possible. If an emergency unblinding occurs, the PSSB will immediately notify the DSMB Chair. The DSMB Chair will determine whether the DSMB members need to be involved immediately versus during the next DSMB meeting.

For the clinical site or the DSMB to request unblinding for a non-emergency situation, the following procedure must be followed for the site to receive approval to unblind the subject's treatment order assignment:

- 1. The PI will send the request to the US Army Medical Materiel Development Activity (USAMMDA), ORA, PSSB ([contact]). The PSSB will notify the PVG MD and the un-blinded Westat Statistician of the request to un-blind. The request must include the subject's identification number, last completed study visit, date of last plasma infusion (or date of last donation visit if no infusion visit has taken place), and an explanation of why unblinding information is requested (eg, subject has experienced a Grade 3 clinical toxicity that is related to the infusion);
- 2. If the PVG MD approves the request to un-blind, authorization will be sent to the unblinded Westat statistician via email;
- 3. If the DSMB requires un-blinded data for Cohort 3, the DSMB Chair will send the request to the PSSB ([contact]). PSSB will notify the Westat un-blinded biostatistician who will provide the un-blinded data directly to the DSMB for review.

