#### 6.10. Trial Treatment Randomization Codes

The data management center for the study will provide a list of the randomized order for administration of FDP and FFP for Cohort 3. Unblinding prior to the end of the study will occur only to protect subject safety.

The codes will be maintained by the website randomization system. The system will only send out website randomization confirmation with unmasked treatment assignment to the personnel that have been designated in the randomization, masking, and unmasking plan. Unblinding will occur at the end of the study after all study data are entered in the database, cleaned, and the database is locked. Study arm assignment information will only be provided to 5th floor HBC FDP research staff.

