# 10.6.3. Reporting Additional Immediately Reportable Events to the Sponsor's Safety Office

#### **10.6.3.1. Pregnancy**

Each pregnancy (for subjects and for female partners of participating male subjects) must be reported by the PI within 72 hours of identification by emailing the Pregnancy Report Form

(FORM.5.2.4) (Appendix K) to the sponsor's safety office (ORA). The incident must also be reported to the local IRB and/or the USAMRMC ORP in accordance with the IRB policy.

Subjects who become pregnant after receipt of investigational product will be withdrawn from the study and followed to term. The following information will be gathered, documented, and reported on the follow-up Pregnancy Report Form: outcome; date and type of delivery; APGAR scores; and health status of mother and child, including the child's gender, height, and weight. Complications and/or abnormal outcomes should be reported including any premature terminations, and are to be followed as above under the AE section. A pregnancy is reported as an AE or SAE only when there is suspicion that the investigational product may have interfered with the effectiveness of contraception or there was a serious complication in the pregnancy, including a spontaneous abortion, an elective termination for medical rationale, or the infant has a congenital anomaly/birth defect.

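### SAP 3.3.2 makes every reported pregnancy a standing reason to break a Cohort 3 code, a ground that protocol 6.6.3 does not contain and that skips its approval step

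*SAP*

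**What the plan says.** SAP 3.3.2 gives a closed list of three reasons for which an individual code may be broken: an emergency or serious condition, a DSMB request, and "Unblinding for all reported pregnancies occurring during the study by the HBC PI". It then refers the reader to protocol 6.6.3 and to a separate Randomization, Masking and Unmasking Plan.

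Protocol 6.6.3 states that, before database lock, "unblinding of a subject's individual randomization code is only to be performed in the case of a medical emergency" or of a serious medical condition, and only "when knowledge of the investigational study product is essential for the clinical management or welfare of the subject". For everything else it has a request procedure: "For the clinical site or the DSMB to request unblinding for a non-emergency situation, the following procedure must be followed". The PI must explain the request, and the decision lies elsewhere: "If the PVG MD approves the request to un-blind, authorization will be sent to the unblinded Westat statistician via email". Protocol 6.10 adds a general limit: "Unblinding prior to the end of the study will occur only to protect subject safety".

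The protocol's own pregnancy section, 10.6.3.1, covers pregnancies of subjects and of male subjects' female partners. It says "Subjects who become pregnant after receipt of investigational product will be withdrawn from the study and followed to term" and mentions no unblinding. On replacement in Cohort 3, protocol 6.6.1 and SAP 3.2 agree that "the replacement subject, assigned a unique SID, will be assigned to the same treatment arm as the discontinued subject".

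Protocol 6.6.2 and SAP 3.3.1 both list the PI and the pharmacovigilance physician as blinded.

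**The concern.** The two documents give different closed lists, so staff holding both cannot follow both when a pregnancy is reported. The SAP treats the break as already approved. The protocol requires either a showing that product knowledge is essential or a reasoned request that someone other than the PI approves.

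What is at stake is assessor blinding in Cohort 3. Under protocol 10.3 and 10.4 the PI assigns relatedness and severity to every adverse event, and the first secondary objective compares FDP with FFP safety within eight subjects. Knowing the sequence tells the PI which infusion was FDP in that subject.

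The scope is also wider than subjects' own pregnancies. A partner's pregnancy is reportable, so it triggers the SAP bullet. No document explains why the order of a man's own plasma products would be needed in that case.

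**Working it through.** The plan states no figure on this point, so the check is a comparison of texts followed by simple sizing.

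**Comparison of grounds**

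1. *Emergency or serious condition.* This is in both documents and they agree.
2. *DSMB request.* SAP second bullet; protocol 6.6.3, third step of the request procedure. They agree.
3. *Pregnancy.* This is the SAP's third bullet. It has no counterpart in protocol 6.6.3, 6.10 or 10.6.3.1.
4. *Other site requests.* Protocol 6.6.3 routes these through the pharmacovigilance physician. The SAP list omits this route, so a pregnancy case under the SAP never meets it.

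**Who learns the code**

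The closing words of the bullet can attach to the unblinding, so that the PI breaks or receives the code, or to the reporting, since protocol 10.6.3.1 makes the PI the reporter. The first reading is likelier in a list of reasons for unblinding. On the second, the recipient is unstated and the approval step is still missing.

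**Completers disclosed per event**

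Inputs: eight Cohort 3 completers, four per sequence, allocated 1:1 (protocol 6.6.1, 7.6.3). Completion means both infusions plus the 7-day visit after the second. Assume the PI learns the code.

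- *Partner pregnancy, subject completes.* He is neither withdrawn nor replaced. One completer is disclosed: 1/8 = 12.5%, or 1/4 = 25% of his sequence.
- *Subject pregnancy after completion.* No replacement; again 1/8.
- *Subject pregnancy before completion.* She is withdrawn and is not one of the eight, although she remains in safety population S1. Her replacement goes to the same arm. If the PI can recognise the replacement, which is likely at one site with eight completers, the probability of naming that subject's sequence rises from 0.5 to 1.0 before the first infusion. The replacement is 1/8 of completers.

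Each event therefore discloses at most one completer. If the disclosed subject is a completer and the final split is held at 4:4, each of the other seven is in the opposite sequence with probability 4/7 = 0.57 rather than 0.50, a small further leak.

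**How often**

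For subjects' own pregnancies before completion, protocol 7.4 defines required contraception as failing in under 1% per year with correct use. Suppose all eight subjects are women of childbearing potential and the exposed period is Day 1 to the nominal Day 22:

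8 × 0.01 × 22/365 = 0.0048 expected pregnancies.

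At an assumed tenfold failure rate the figure is 0.048. Partner pregnancies are not bounded in this way, because the eligibility criteria set no contraceptive requirement for male subjects.

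**The case against.** The strongest reply is that the protocol does not prohibit unblinding for a pregnancy. Its non-emergency route could permit any single case, and the unmasking plan cited by the SAP, which is not among the documents reviewed, may set the approver and recipient. The first part stands: a reader might infer that the protocol bars every such break, and it does not. What it lacks is an automatic break for all pregnancies. The unseen plan may add detail, but it cannot make two different closed lists agree.

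A second reply is that the code can matter. This also stands in part. A reader might infer that the sequence never carries exposure information because every completer receives both products. That is true only after infusion 2. A pregnancy test is scheduled before infusion 2, and a subject found pregnant then has had one product only. Protocol 5.6.1.5 describes the risk to an unborn child as unknown and ties its advice on avoiding pregnancy to the last FDP infusion. So some breaks may be justified, which is a reason to decide them case by case. The pregnancy form in Appendix K asks for dose dates, number of doses, causality and action taken, but not for product or order.

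Third, the replacement leak is not specific to pregnancy. It follows any code break before completion, including the emergency breaks that the protocol permits. That is correct, and it means the leak cannot carry this point by itself.

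Finally, the analyses are descriptive with no hypothesis test, and the research monitor reviews all adverse events. Both limit the consequence. However, descriptive comparisons of eight subjects still rest on how events are graded, and it is the PI who grades them.

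**Conclusion.** The inconsistency is in the text on either reading of the bullet and should be reconciled. SAP 3.3.2 gives standing approval for a break that protocol 6.6.3 would allow only on necessity or on approved request, and on the likelier reading it discloses the sequence to the blinded assessor.

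The size is modest. Only Cohort 3 is affected, at most one of eight completers is disclosed per event, and events should be rare. This rests on the PI learning the code and, for a replacement, on the PI recognising that subject.

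Two stronger conclusions are not supported. A reader might count two of the eight completers as lost to a single pregnancy, but a subject withdrawn before completion is not one of the eight. A reader might also conclude that the same-arm replacement rule should go. Protocol 7.6.3 and SAP 3.4 treat that rule as needed for the 1:1 ratio, and changing it would require a protocol amendment and could leave the sequences at 5:3. Removing the automatic break closes the pregnancy-driven leak without that cost.

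**What to change.** In SAP 3.3.2, either delete the pregnancy bullet or make it subject to the protocol 6.6.3 request-and-approval route, so that no pregnancy, whether a subject's or a partner's, triggers automatic unblinding. Bring the unmasking plan into line if it repeats the bullet.

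Add one sentence: where exposure information is needed for a pregnancy report, the unblinded statistician releases it only to a named recipient who is neither the PI nor the pharmacovigilance physician. The second exclusion matters because that physician works within the sponsor's safety organisation, is blinded, and makes the final relatedness decision on serious events. Sending the code to the safety office without naming a recipient could therefore unblind a second assessor.

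Leave the same-arm replacement rule unchanged.

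The cost is a small SAP edit and, in use, one approval step for a pregnancy case. Sample size, visits and analyses are unaffected.
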